### ***21.3 Collection and management of adverse events***

The frequency of adverse events (e.g., sleep disturbance, cool or mottled extremities, diarrhea, etc.) were collected by the investigator and reported by parents. The investigators collected any untoward medical occurrence in the form of signs, symptoms, abnormal laboratory findings, or diseases that emerged or worsened relative to baseline assessment. All adverse events that were identified by the investigators as at least possibly treatment-related (treatment-emergent adverse events or adverse events that have worsened since baseline) were included in the analysis. For each adverse event, the percentage of subjects who experienced at least 1

---

occurrence of the given event was summarized by treatment group. Adverse events during the initial 24-week treatment phase were compared between the two groups.

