**11 Exclusion Criteria:**

- (1) Patients contraindicated for the administration of  $\beta$ -blockers, such as those with an allergy or hypersensitivity to propranolol; hypoglycemia ( $<40$  mg/dL); hypotension ( $<50/30$  mmHg); severe bradycardia ( $<80$  bpm); second- to third-grade atrioventricular block; heart failure; bronchial asthma or bronchial obstruction.
- (2) Patients with any acute illness or gastrointestinal diseases, especially one interfering with normal oral intake.
- (4) Patients with inadequate liver function:  
Total bilirubin higher than or equal to  $1.5 \times$  the upper limit of the normal (ULN) for age and alanine aminotransferase and aspartate aminotransferase higher than or equal to  $2.5 \times$  the ULN for age.
- (5) Patients with inadequate renal function:  
Serum creatinine higher than or equal to 0.8 (mg/dL).
- (6) Patients diagnosed with deep IH, congenital hemangioma, Kaposiform hemangioendothelioma, tufted angioma, or other vascular anomalies.
- (7) Patients previously treated with any IH therapies, including corticosteroids, propranolol, atenolol, topical timolol, captopril, itraconazole, imiquimod, vincristine, interferon- $\alpha$ , laser therapy or other treatments.
- (8) Indication for treatment with corticosteroids, captopril, itraconazole, imiquimod, vincristine, interferon- $\alpha$ , sirolimus, or tacrolimus for an indication other than IH.
- (9) Indication for treatment with a beta-blocker for an indication other than IH.
- (10) Patients who received the following drugs within the 1 week before enrollment:  $\beta$ -AR agonists, such as epinephrine, norepinephrine and salbutamol, etc.; or other cardiovascular agents, including but not limited to calcium channel blockers, ACE inhibitors and inotropic agents, etc.
- (11) Patients with an inability to participate in or follow-up during the study treatment and assessment plan.

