## 15 Pretreatment evaluations

(1) At the initial visit, investigators collected demographic and clinical data. The patients' parents who opted for oral  $\beta$ -blocker therapy provided a thorough medical history (e.g., existence of comorbidities) and family history (e.g., cardiovascular disease).

Acquisition of general information:

- Sex;
- Gestational age;
- Date of birth;
- Age,
- Body weight.

Hemangioma histories were also taken from families, including:

- Age when the hemangioma appeared;
- Changes in the color of the hemangioma; and
- The period during which the hemangioma showed the greatest growth before referral.

(2) In all infants, the following inspections were performed before enrollment:

- Heart rate;
- Blood pressure;
- Blood glucose;
- Full blood count;
- Liver function tests;
- Renal function
- Electrocardiogram (ECG); and
- Echocardiogram.

If cardiovascular abnormalities were detected, the patient were evaluated by pediatric cardiologists to ensure that it would be safe to initiate  $\beta$ -blocker treatment. Echocardiographic findings, such as a false tendon in the left ventricle, a patent ovale, left superior vena cava to the coronary sinus, and small systemic-to-pulmonary arterial collateral vessels, were considered normal variants and are not reported as anomalies.

(3) When patients had more than one IH, detailed information was obtained for the most clinically important hemangioma (typically the largest or most ulcerated lesion). Hemangioma assessments included lesion size, lesion location, stage of growth,

---

morphologic subtypes, depth of involvement, and treatment indication.

(4) According to Chang et al., lesion size was recorded using 'hemispheric' measurement. A soft tape measure was draped over the hemangioma, and the longest diameter and a measurement perpendicular to it were noted to obtain a measurement in cm^2.

(5) Hemangioma lesions were classified by morphologic subtypes:

-Localized: well-defined focal lesions;

-Segmental: a hemangioma involving an anatomic region that was often plaque-like and often measured at >5 cm in diameter; or

-Indeterminate: neither clearly localized nor segmental.

(6) Hemangioma lesions were also be classified by soft-tissue depth:

-Superficial, which was defined as red with little or no evidence of a subcutaneous component;

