## ***20.3 Quality of life***

---

Quality of life (QOL) was measured at baseline and week 48.

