### ***21.2 Outpatient monitoring***

The patients' parents or guardians were asked to inform the investigators about adverse events at any time to ensure that potential adverse events could be handled promptly and appropriately. Parents or guardians were also provided with a patient booklet to record any possible adverse events during treatment. Data on adverse events was obtained at scheduled or unscheduled study visits based on information spontaneously provided by the subject and/or through questioning of the participant. Each scheduled visit included an evaluation of efficacy and routine examination. Routine examinations included physical examination, electrocardiography, routine blood tests, and blood glucose measurement.

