#### ***21.4 Definition of adverse events***

Identified adverse events were coded using the latest version of the Medical Dictionary for Regulatory Activities. Adverse events included suspected adverse drug reactions, other medical experiences, regardless of their relationship with the investigative drugs, such as infections, injury, surgery, accidents, extensions of symptoms or apparently unrelated illness, and significant abnormalities in clinical laboratory values or physical examination findings. These medical conditions relate to the disease under study whose changes during the study are consistent with natural disease progression. Therefore, they are not considered adverse events, but they shall be recorded by the investigators. Medical conditions that were present at baseline shall not be considered adverse events unless worsening occurred.

Blood pressure and heart rate values were compared with age-related reference ranges: hypotension was defined as an SBP less than 50 mmHg and/or a DBP less than 30 mmHg; bradycardia was defined as an HR less than 80 beats per minute (bpm) while awake or less than 60 bpm while asleep.

Intolerable CNS-related adverse effects (e.g., sleep disturbance and agitation) were defined as adverse events that did not disappear or were not relieved after treatment administration was altered (e.g., earlier evening dose or a decrease in daily dose). Sleep disturbance was characterized by difficulty in falling sleep and/or remaining sleep, or development of increased waking or night terrors. Agitation was characterized by a state of restlessness associated with unpleasant feeling of irritability and tension.

Bronchial irritation was classified as hyperreactivity, bronchospasm, bronchiolitis, and cold-induced wheezing.

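### Adverse events must be new or worse than baseline, but no structured pre-randomisation record of sleep or agitation is specified, so unblinded parents and investigators judge new-or-worse status without a recorded comparator

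*Combined protocol and SAP*

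**What the plan says.** The event rule is relative to a starting state. Section 21.3 covers signs, symptoms, abnormal laboratory findings or "diseases that emerged or worsened relative to baseline assessment". Section 21.4 adds: "Medical conditions that were present at baseline shall not be considered adverse events unless worsening occurred". Section 21.4 also defines sleep disturbance partly as a change, since an increase in waking qualifies. Section 21.3 compares events between arms over the first 24 weeks, and Section 21.6 classes intolerable CNS effects as serious.

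The starting state is set out in Section 15. Parents "provided a thorough medical history (e.g., existence of comorbidities) and family history (e.g., cardiovascular disease"). Demographics and hemangioma history follow, and then: "In all infants, the following inspections were performed before enrollment", leading to a list of heart rate, blood pressure, glucose, blood count, liver and renal function, ECG and echocardiogram. Sleep and agitation are not listed.

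For outpatients, Section 21.2 says: "Parents or guardians were also provided with a patient booklet to record any possible adverse events during treatment". Visit data come from spontaneous report or questioning. The trial is open-label; Section 6 masks outcome assessors only, and the blinding described in Section 18 concerns the photographs. Under Section 21.5 the investigators judge causality, and only events at least possibly related to treatment are analysed.

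**The concern.** Section 5 gives fewer CNS effects, with sleep disturbance and agitation as examples, among the reasons to consider atenolol. These effects are reported by parents, in infants enrolled at 5 to 20 weeks of age, some of whom may already wake often or be unsettled. Whether such an infant enters the event count depends on a before-and-after comparison for which the plan specifies no recorded before.

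The comparison is then made by people who know the drug and, under Section 21.7, have discussed its possible side effects before treatment. Two consequences follow. If pre-existing symptoms are miscounted as new equally in both arms, the difference between arms shrinks. If they are miscounted more often in one arm, the comparison is biased. Randomisation balances pre-existing symptoms in expectation, but not how unblinded reporters classify them.

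**Working it through.** **Step 1. Compare what the rule needs with what is recorded before treatment.**

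| Event type | Starting state in the plan |
|---|---|
| Heart rate, blood pressure, glucose | Measured before enrolment (Section 15) and before the first dose (Section 21.1) |
| Laboratory values, ECG | Measured before enrolment (Section 15) |
| Breathing | No symptom item; "bronchial asthma or bronchial obstruction" is an exclusion (Section 11) |
| Stool | No symptom item; Section 11 excludes "Patients with any acute illness or gastrointestinal diseases, especially one interfering with normal oral intake" |
| Sleep, agitation | No listed item and no related exclusion |

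The gap is complete for sleep and agitation. It is partial for breathing and stool.

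**Step 2. Look for another source of a starting state.** The medical history is open-ended and prescribes no symptom questions. The Protocol outline mentions a baseline survey without describing its content. Section 20.3 says: "Quality of life (QOL) was measured at baseline and week 48"; week 48 lies outside the 24-week comparison, the wording of the four patient physical-symptom items is not given, and no link to adverse-event classification is stated.

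**Step 3. Illustrate the effect.** The plan has no figure to reproduce here. The only input from the documents is 180 infants per arm (Section 12). All the rates below are assumptions.

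Let t be the true new-onset rate, p the proportion with pre-existing symptoms, and m the share of those miscounted as new. Then

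observed rate = t + (1 − t) × p × m.

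Rejection probabilities are for a two-sided z-test of two proportions at 0.05 with 180 per arm.

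*Unequal handling.* True rate 10% in both arms; m = 30% on propranolol and 10% on atenolol.
- p = 10%: 0.10 + 0.90 × 0.10 × 0.30 = 12.7%, against 0.10 + 0.90 × 0.10 × 0.10 = 10.9%. Difference 1.8 points; false significance about 8%.
- p = 20%: 15.4% against 11.8%. Difference 3.6 points; false significance about 17%.
- p = 40%: 20.8% against 13.6%. Difference 7.2 points; false significance about 44%.

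*Equal handling, no true difference.* With m equal in both arms the expected difference is zero and the error rate stays near 5%. Both rates are inflated.

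*Equal handling, true 20% against 10%.* Power with no miscounting is 77%.
- p = 10%, m = 25%: 22.0% against 12.25%. Difference 9.75 points; power about 70%.
- p = 20%, m = 25%: 0.20 + 0.80 × 0.20 × 0.25 = 24.0%, against 0.10 + 0.90 × 0.20 × 0.25 = 14.5%. Difference 9.5 points; power about 63%.
- p = 40%, m = 50%: 36.0% against 28.0%. Difference 8.0 points; power about 37%.

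The false-significance figures are driven by the assumed threefold difference in m. They show direction and sensitivity, and do not estimate what happened in this trial.

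**The case against.** The best defence is that the plan is not silent about baseline. It requires a thorough medical history, for which comorbidities are only an example; it has a baseline survey and baseline quality-of-life forms whose content is not shown; and enrolment is itself a scheduled visit, with a routine examination under Section 21.2. Sleep may have been asked about. That stands as a limit: the documents show that no structured record is specified, not that no site ever made one.

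A reader might infer three stronger things.

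- *That breathing and stool are equally without a baseline.* The exclusions for airway disease, acute illness and gastrointestinal disease give a coarse starting state. Section 21.4 also classifies bronchial irritation by clinical categories rather than by a parent's impression of change.
- *That recall alone decides what counts.* The booklet lets parents record events as they occur, the first visit is at one week, and investigators apply a relatedness filter. Intolerable CNS effects are defined by persistence after administration is altered, which depends less on a pre-treatment sleep record. The recall problem is confined to the parent-reported state before treatment. Nor is it stated when the booklet is handed out; its coverage is described only as the treatment period.
- *That the main safety comparison is shown to favour atenolol falsely.* The plan designates no main safety endpoint. Nothing in the documents shows that handling differed by arm, and the direction in the illustration is assumed.

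A last objection is that a baseline form leaves the on-treatment answers with the same unblinded parents. That is correct and limits what the fix can achieve.

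**Conclusion.** The concern holds for sleep and agitation. The plan's own definition requires a comparison with baseline, and no structured baseline is specified for the parent-reported CNS effects that form part of the rationale for atenolol. Unblinded parents and investigators therefore judge whether such a symptom is new or worse without a recorded comparator.

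The documents do not fix the size, because neither the prevalence of pre-existing symptoms nor the rate of misattribution is given. Under the assumed rates, the spurious difference ranges from 1.8 to 7.2 points with unequal handling. With equal handling, power falls from 77% to between 37% and 70%. If pre-existing symptoms are rare and handled alike, the effect is small. The textual finding does not depend on these figures. It is a worthwhile, inexpensive improvement in data collection, and it does not show that the safety comparison is invalid.

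**What to change.** Add to Section 15(1) a few fixed parent questions on sleep, night waking and agitation, with a stated look-back period, completed for every infant before randomisation. Wheeze or cough, stool frequency and cold extremities could be added as options. Repeat the same questions at the existing visits at weeks 1, 4, 12 and 24. State in Sections 21.3 and 21.4 that these events are classified as treatment-emergent only if new or worse than the recorded pre-randomisation answer.

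The cost is a few form items and a small burden on parents, with no extra visits. The baseline answer is given before the arm is known, so knowledge of the drug cannot affect it; the later answers are still open-label. Because infant sleep changes with age, a single early answer is also an imperfect comparator over 24 weeks. The change reduces the problem but does not remove it.

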#### ***21.4 Definition of adverse events***

Identified adverse events were coded using the latest version of the Medical Dictionary for Regulatory Activities. Adverse events included suspected adverse drug reactions, other medical experiences, regardless of their relationship with the investigative drugs, such as infections, injury, surgery, accidents, extensions of symptoms or apparently unrelated illness, and significant abnormalities in clinical laboratory values or physical examination findings. These medical conditions relate to the disease under study whose changes during the study are consistent with natural disease progression. Therefore, they are not considered adverse events, but they shall be recorded by the investigators. Medical conditions that were present at baseline shall not be considered adverse events unless worsening occurred.

Blood pressure and heart rate values were compared with age-related reference ranges: hypotension was defined as an SBP less than 50 mmHg and/or a DBP less than 30 mmHg; bradycardia was defined as an HR less than 80 beats per minute (bpm) while awake or less than 60 bpm while asleep.

Intolerable CNS-related adverse effects (e.g., sleep disturbance and agitation) were defined as adverse events that did not disappear or were not relieved after treatment administration was altered (e.g., earlier evening dose or a decrease in daily dose). Sleep disturbance was characterized by difficulty in falling sleep and/or remaining sleep, or development of increased waking or night terrors. Agitation was characterized by a state of restlessness associated with unpleasant feeling of irritability and tension.

Bronchial irritation was classified as hyperreactivity, bronchospasm, bronchiolitis, and cold-induced wheezing.

#### ***21.5 Relationship of adverse events***

All adverse events were collected and graded according to Common Terminology Criteria for Adverse Events, version 4.0 (CTCAE v4.0). The investigators evaluated each adverse event that occurred after administration of  $\beta$ -blockers regarding the relationship with the administration of  $\beta$ -blockers. The causality of the adverse event was determined by the investigators and classified as definitively not related,

---

probably not related, possibly related, probably related, or definitively related. Only patients with events that were at least possibly treatment-related were taken into consideration:

(1) Definitively not related: only a remote connection exists between the administration of  $\beta$ -blocker and the reported adverse event. Other conditions, including concurrent illness, progression or expression of the disease state or reaction of the concomitant medication, appear to explain the reported adverse event.

(2) Most likely, not related: an adverse event that does not follow a reasonable temporal sequence related to the administration of  $\beta$ -blocker and is likely to have been produced by the patient's clinical state, other modes of treatment or other known etiology.

(3) Possible related: an adverse event that has a reasonable possibility that the event may have been caused by the administration of  $\beta$ -blocker. The adverse event has a timely relationship to the administration of  $\beta$ -blockers. However, the pattern of response is atypical, and an alternative cause seemed more likely, or there is significant uncertainty about the cause of the event.

(4) Probable related: an adverse event that has a reasonable possibility that the event is likely to have been caused by the administration of  $\beta$ -blocker. The adverse event has a timely relationship and follows a known pattern of response, but a potential alternative cause may be presented.

(5) Definitely related: there is a reasonable possibility that the event might have been caused by the administration of  $\beta$ -blocker. A certain event has a strong temporal relationship, and an alternative cause is unlikely.

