### ***25.5 Safety outcome analyses***

All safety outcomes were analyzed based on the safety population, which comprises all patients who were treated with at least one dose of trial treatment and included in a treatment group.

All premature study discontinuations are listed along with treatment group, time in study and reason for discontinuation.

Unless specified otherwise, no data imputation was applied for missing safety evaluations. For analysis and reporting purposes, partial dates for adverse events and concomitant therapies were imputed.

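### The between-arm adverse event comparison appears limited to events that unblinded investigators judge at least possibly drug-related, and no all-causality comparison is stated

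*Combined protocol and SAP*

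**What the plan says.** All references are to the combined protocol and SAP.

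- **Collection is broad.** Section 21.3: "The investigators collected any untoward medical occurrence in the form of signs, symptoms, abnormal laboratory findings, or diseases". Section 21.5: "All adverse events were collected and graded according to Common Terminology Criteria for Adverse Events". Section 21.4 defines adverse events without regard to their relation to the drugs.
- **Analysis is narrow.** Section 21.3 takes into the analysis the events that investigators identified as at least possibly related. A parenthesis then explains that phrase differently: "treatment-emergent adverse events or adverse events that have worsened since baseline) were included in the analysis". By-group percentages follow, and then: "Adverse events during the initial 24-week treatment phase were compared between the two groups".
- **The limit is repeated.** Section 21.5: "Only patients with events that were at least possibly treatment-related were taken into consideration". Section 16 uses the same relatedness wording when it describes what is collected in the 24 weeks.
- **Who decides.** Section 21.5: "The causality of the adverse event was determined by the investigators". It uses five classes, two of them for unrelated events.
- **Blinding.** The protocol outline and section 6 call the trial open-label, with masking of outcome assessors. The only blinded assessors described (sections 18, 20.1 and 20.6) read photographs.
- **Safety analysis.** Section 25.5: "All safety outcomes were analyzed based on the safety population". It defines which patients are analysed, not which events, and states no comparison regardless of cause.

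**The concern.** Two things are wrong.

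First, an event counts in the comparison only after someone who knows the drug has decided that the drug may have caused it. Section 5 argues for atenolol because it may have fewer central nervous system effects and little beta-2 activity at low dose. An investigator with that expectation may attribute a disturbed night or a wheeze more readily to propranolol than to atenolol. The table would then show a difference in attribution as if it were a difference in incidence. Randomization does not protect against this, because the selection happens after the drug is known.

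Second, the analysed set is not uniquely defined. A treatment-emergent event is one that is new or worse since baseline. A treatment-related event is one that someone believes the drug caused. Section 21.3 uses the first to explain the second, and two analysts could build different tables from it.

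The safety comparison is half of the trial's stated purpose. A reader who sees only related events cannot tell whether the result depends on the attribution step.

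**Working it through.** **Step 1. Which events are compared?** The documents give no figure to reproduce here, so the sections are set side by side.

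| Section | Points to related events only | Points to all treatment-emergent events |
|---|---|---|
| 21.3, inclusion sentence | its main clause | its parenthesis |
| 21.3, comparison sentence | follows directly on the inclusion rule | names adverse events without a condition |
| 21.5 | restricts explicitly ("Only patients with events that were at least possibly treatment-related were taken into consideration") | none |
| 16 | same relatedness wording | none |
| 25.5 | silent | silent |

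The related-only reading has the better support, and nowhere is an all-causality comparison stated. Section 16 could suggest that collection is limited too. It does not exclude other events, though, and section 21.5 provides classes for unrelated ones, so this looks like loose wording.

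**Step 2. How much could the filter matter?**

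Inputs:
- n = 180 per arm (section 12).
- Two-sided 0.05 per event type. Section 25.5 names no test; section 25.4 names Fisher's exact or chi-square for categorical secondary outcomes.
- True incidence π, equal in both arms: assumed, 2% to 40%.
- Attribution a_P (propranolol) and a_A (atenolol), the share of events called at least possibly related: assumed.

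Analysed rates: p_P = π·a_P and p_A = π·a_A.

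For the z test with pooled variance, p̄ = (p_P + p_A)/2, SE0 = √[2p̄(1−p̄)/n] and SE1 = √[(p_P(1−p_P) + p_A(1−p_A))/n]. With d = p_P − p_A:

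P(p<0.05) ≈ Φ[(d − 1.96·SE0)/SE1] + Φ[(−d − 1.96·SE0)/SE1].

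Worked case, π = 20%, attribution 80% v 60%:
- p_P = 0.20 × 0.80 = 0.16 and p_A = 0.20 × 0.60 = 0.12. Expected counts are 28.8 v 21.6, and d = 0.04.
- p̄ = 0.14; SE0 = √(2 × 0.14 × 0.86/180) = 0.0366; SE1 = √[(0.1344 + 0.1056)/180] = 0.0365.
- Φ[(0.04 − 0.0717)/0.0365] + Φ[(−0.04 − 0.0717)/0.0365] ≈ 0.193 + 0.001 = 0.194.
- Fisher's exact test, by full enumeration of both binomials: 0.153.

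Chance of nominal p<0.05 when the true incidences are equal (z / Fisher):

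| Attribution, propranolol v atenolol | 2% | 5% | 10% | 20% | 40% |
|---|---|---|---|---|---|
| 80% v 60% | 6.2 / 1.2% | 8.1 / 4.1% | 11.5 / 7.8% | 19.4 / 15.3% | 39.3 / 35.0% |
| 80% v 70% | 5.3 / 1.1% | 5.7 / 2.8% | 6.5 / 4.1% | 8.3 / 6.1% | 13.1 / 10.8% |
| 95% v 85% | 5.2 / 1.4% | 5.6 / 3.0% | 6.3 / 4.1% | 7.8 / 6.0% | 12.4 / 10.5% |
| 95% v 90% | 5.1 / 1.4% | 5.1 / 2.7% | 5.3 / 3.4% | 5.7 / 4.2% | 6.8 / 5.5% |
| 100% v 100% | 5.0 / 1.5% | 5.0 / 2.7% | 5.0 / 3.2% | 5.0 / 3.7% | 5.0 / 3.8% |

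The effect is material only when the event is common and the attribution gap is large. Hypoglycemia and bronchial hyperreactivity, which section 5 calls rare, belong in the left-hand columns.

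**The case against.** The best reply is that the parenthesis in section 21.3 states the real intent, namely all treatment-emergent events, so that the problem is one of wording. This cannot be ruled out. But section 21.5 restricts explicitly and carries no such parenthesis, so under that intent section 21.5 needs correcting.

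The second reply is that the filter hardly binds. The possible class takes in an event even where "an alternative cause seemed more likely, or there is significant uncertainty about the cause of the event", the same scale serves both arms, and infants are dosed daily for at least six months, so timing would rarely exclude an event. This has force: it makes the 95% v 90% row as plausible as the 80% v 60% row, and there the inflation is negligible. It is not complete, because events that the investigator ascribes to concurrent illness still drop out. The direction is also inferred: with little comparative data, an investigator might attribute events more cautiously to either drug.

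Third, there are partial safeguards. Hypotension and bradycardia have numeric thresholds (21.4), glucose is measured by glucometer (21.1), and the serious-event definition carries no relatedness condition (21.6). Dose changes are recorded (21.7), time to treatment discontinuation is plotted (25.4), and premature study discontinuations are listed by group with reasons (25.5). These narrow the gap, but none is a by-arm comparison of events regardless of cause.

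Finally, an all-causality table does not cure unblinded reporting by parents and investigators, and background illness can dilute a true difference. Both points stand. They are reasons to keep both tables.

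**Conclusion.** The concern holds, as a change that should be made. On the better-supported reading, the week 0–24 safety comparison counts only events that unblinded investigators judge at least possibly related, and no all-causality comparison is stated. Bias is possible, not demonstrated. Its size rests wholly on assumed incidence and attribution rates: from practically nothing (5.7% against 5.0% by z test at 20% incidence with 95% v 90%) to a spurious 4-point difference and a 15% to 19% false-positive chance per event type at 80% v 60%, and more for commoner events. Confidence is medium, because the parenthesis in section 21.3 leaves the intended set open. The ambiguity needs repair under either reading. The primary outcome, read from photographs by blinded assessors, is not affected.

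**What to change.** 1. In section 25.5, make the main by-arm comparison all treatment-emergent adverse events (new or worsened since baseline), regardless of causality, in the safety population over weeks 0–24. Keep the table of at least possibly related events as secondary.
2. In section 21.3, remove the parenthesis that equates related with emergent, and define the two terms separately. Reword section 21.5 so that its restriction applies only to the secondary table.
3. Align section 16 with sections 21.3 to 21.5, so that it says all adverse events are recorded whatever their cause.

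The cost is low: extra tables and some rewording. Sections 21.2 to 21.5 indicate that the events are already collected, graded and classified by causality, so no new data are needed. The price is more noise from ordinary childhood illness in the main table, which the secondary table helps to interpret. Unblinded reporting remains and should be acknowledged as a limitation.
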